This is an open label pilot study in which we will consent up to 25 subjects in order to treat 10 eligible subjects with probable mild to moderate AD. The study is single site and non-randomized. The subjects will be given rifaximin 550 mg orally twice daily for 3 months after evaluation to ensure they have no contraindications. Subjects at risk for drug interactions or tolerability issues may be started and/or maintained on a lower dose of 550 mg once a day. Individuals on concomitant drugs which are contraindicated per the package insert or in the investigators judgment will be excluded. Individuals on concomitant drugs which are not contraindicated but known to elevate blood levels SIGNIFICANTLY OR THOSE WITH MILD AEs (E.G. MILD DIARHEA) WILL receive qd dosing BASED ON CLINICIAN JUDGMENT. Consent, demographics, history, list of current medications, clinical and safety assessments, MMSE and blood tests (CBC, CMP, TSH, B-12 and Folic acid) will be performed at the Screening Visit. Medical history, physical exam, serum neuronal biomarkers and cytokines, serum ammonia level, Adverse Events and cognitive testing (ADAS-Cog-11) will be performed at the Baseline Visit. A stool sample collection kit will also be given to the subject and caregiver at the Baseline Visit, with instructions for use and how to get the sample back to the research coordinator. The stool sample will be obtained prior the subject taking the study drug. Medical history, physical exam, serum neuronal biomarkers and cytokines, serum ammonia level, Adverse Events and cognitive testing (ADAS-Cog-11) will be performed at the 3 month endpoint visit. A stool sample collection kit will also be given to the subject and caregiver at the baseline visit and 3 month Visit with instructions for use and how to get the sample back to the research coordinator. Interim safety checks will occur via phone calls one week after baseline and then every 2 weeks until the 3 month visit, which will then be followed by a 5 month phone call. Caregivers will be instructed to call the research coordinator or the PI ([name] after business hours or on weekends) if any change in stool is noticed at any time during the study. Unscheduled visit/labs may occur if warranted for safety based on clinical judgment. Because of a small risk of developing *C. difficile* up to 2 months following the last administration of rifaximin, the subjects will be followed for an additional 2 months after the 3 month treatment ends. Subjects who terminate early will receive the 3 month assessment at the time of termination.

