
Scientific Rationale for Study Design

This is an open label pilot study designed to provide preliminary evidence on the clinical efficacy of rifaximin in improving cognition in AD patients. We will be looking for improvement in test scores, changes in serum levels of neuronal markers and cytokines and changes in gut microbiota following treatment. We will also be collecting data

regarding the safety of long-term use of this non-absorbed antibiotic for this disease. This pilot may form the basis for a future larger randomized, double blind controlled study to further test this hypothesis. Statistical analyses will combined subjects on QD and BID for analyses as this is a pilot study and both doses may impact gut flora. In posthoc analyses we will put dosing as a covariate to examine dose effects.

Justification for Dose and Study Population

The rifaximin dosage and route of administration are the same as that used to treat hepatic encephalopathy, for which the drug and dosage are FDA approved. The dose will remain the same throughout the 3 month study of rifaximin administration unless stopped for safety reasons. The dose can be stopped or temporarily reduced for safety or tolerability reasons based on clinical judgment. The age and study sample of mild to moderate probable AD is similar to that used in AD prior trials. We will select our sample to be medically stable and free of hepatic disease and not having had recent antibiotic therapy to minimize risk for C Difficile infection.

End of Study Definition

The end of the study will occur 5 months after baseline testing and first administration of the drug. While drug administration will conclude and endpoint testing will be done at 3 months, we will continue to follow each subject for an additional 2 months, as C. difficile infectious diarrhea can occur up until 2 months after stopping an antibiotic.

Study Population

Inclusion Criteria

Subjects who meet the following criteria will be considered eligible to participate in the clinical study:

Probable Alzheimer's disease (National Institute of Neurological Disorders and Stroke (NINDS) criteria), mild to moderate severity

Ages 55-85; both genders

Mini Mental State Exam (MMSE) scores 10-22

Willing and able to comply with all scheduled clinic visits.

Stable medical health

Has a family or professional caregiver who has regular contact with subject

Ability to consent or legal guardian who can consent

Living at home or in a facility

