The subject may take concomitant medications that do not interact with rifaximin. These medications will be recorded at baseline. Any new medications taken during the study period will be recorded.

Rescue Medicine. AEs will be treated as appropriate with rescue medications.

Participant Discontinuation and Participant Discontinuation / Withdrawal

Discontinuation of Study Intervention

Administration of rifaximin will be discontinued and the study will be halted if a subject develops a severe hypersensitivity to rifaximin or if a subject develops a C. difficile infectious diarrhea with complications or any other AE felt by the clinician to warrant discontinuation.

Participant Discontinuation / Withdrawal from the Study

While subjects are encouraged to complete all study evaluations, they may withdraw from the study at any time and for any reason. Every effort will be made to determine why any subject withdraws from the study prematurely. This information will be recorded. All subjects who withdraw from the study with an ongoing AE will be followed until the event is resolved or deemed stable. If a subject withdraws prematurely, all data normally collected at the 3 month Visit will be collected at the time of premature discontinuation. Subjects who had to interrupt taking the study drug for any reason may be asked to go back on drug if there are no contraindications. Subject participation may be terminated prior to completing the study for any of the following reasons:

- Adverse event
- Protocol violation
- Loss to follow up
- Subject withdrew consent at own request
- Other

A Case Report Form (CRF) page will capture the date and the specific underlying reason for discontinuation of study intervention or participant discontinuation/withdrawal.

Study Assessment and Procedures

Efficacy Assessments

Rifaximin Alzheimer's Disease Study Pro00093318

	V1	V2							V3	V4/End	
Procedures	Screening	Baseline	wk 1	wk 3	wk 5	wk 7	wk 9	wk 11	WK 12 3 months	WK 20 5 months	Early Term
Consent	X										
Medical History	X	X							X		X
Concomitant Medications	X	X							X		X
Vitals	X	X							X		X
VeniPuncture	X								X		X
Blood Tests	X								X		X
Stool Sample		X							X		X
Physical Exam	X								X		X
MMSE	X								X		X
ADAS-COG-11		X							X		X
Study Medication Dispensation		X									
Study Medication Accountability									X		X
AE assesment	X	X	X	X	X	X	X	X	X	X	X
Phone Assessment			X	X	X	X	X	X		X	
Subject compensation		X							X	X	X
OnCore Status update	X									X	

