Phone Screening											
Bristol Stool Question		X							X		X

Unscheduled visit/labs may occur if warranted for safety based on clinical judgment.

Adverse Event Reporting

AE reporting will begin at the time of signing of the informed consent (Screening) and will continue until discharge from the study (5 months after the first administration of rifaximin).

Serious Adverse Event Reporting

The PI will notify the IRB of any SAE, whether deemed rifaximin related or not, that a subject experiences during their participation in the study within 24 hours of becoming aware of the event. Following the end of the subject's 3 month participation in the study, the PI will report SAE's spontaneously if considered at least possibly related to rifaximin. SAE reporting will follow Duke IRB requirements.

All SAE's will be followed until satisfactory resolution or until the site investigator deems the event to be chronic or the participant is stable.

Reporting Events to Participants

Subjects and their caregivers will be informed about individual or aggregate AE's, SAE's and study related results as per IRB guidelines.

Reporting of Pregnancy

NA. Subjects will not be of child bearing age.

Definition of Unanticipated Problems

Unanticipated problems in this study will be any AE's or SAE's not previously described in other investigators' research with rifaximin or not listed on the package insert for rifaximin.

Unanticipated Problem Reporting

Unanticipated problems will be reported to the IRB within 24 hours of its occurrence.

Reporting Unanticipated Problems to Participants

Unanticipated problems encountered during the study will be relayed to the subject(s) if relevant to the subject's safety as deemed appropriate by the Duke IRB.

Supporting Documentation and Operational Considerations

Regulatory, Ethical and Study Oversight Considerations

Informed Consent Process

Before each subject is enrolled in this study, written informed consent will be obtained from the subject and/or legally acceptable representative (LAR) according to local IRB requirements.

Abbreviations

AD	Alzheimer's Disease
AE	Adverse Event
FDA	Food and Drug Administration
IRB	Institutional Review Board
LAR	Legally Acceptable Representative
PI	Principle Investigator
SAE	Serious Adverse Event
US	United States

References:

1. Seiler N. Is Ammonia a pathogenetic factor in Alzheimer's Disease? *Neurochemical Res.* 1993;18:235-245

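### Early terminators have no planned contact in the 2-month C. difficile window that justifies the follow-up, and months 3 to 5 carry two conflicting SAE reporting rules

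*Protocol*

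**What the plan says.** **Reason for follow-up.** Protocol, Study Design, Overall Design, puts the C. difficile risk at "up to 2 months following the last administration of rifaximin". End of Study Definition repeats that "infectious diarrhea can occur up until 2 months after stopping an antibiotic".

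**Length of follow-up.** Overall Design says that "the subjects will be followed for an additional 2 months after the 3 month treatment ends". End of Study Definition says: "The end of the study will occur 5 months after baseline testing and first administration of the drug". It also promises the extra two months to every subject.

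**Early termination.** Overall Design: "Subjects who terminate early will receive the 3 month assessment at the time of termination". Participant Discontinuation / Withdrawal from the Study: "all data normally collected at the 3 month Visit will be collected at the time of premature discontinuation". The same section follows a subject who withdraws with an AE in progress until that event resolves or is stable. In the schedule of assessments, the Early Term column has an AE assessment but no phone assessment. Phone assessments are marked at Weeks 1, 3, 5, 7, 9, 11 and 20 only.

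**Event reporting.** Under Adverse Event Reporting, AE collection "will continue until discharge from the study (5 months after the first administration of rifaximin". Under Serious Adverse Event Reporting, all SAEs are reported while the subject participates. After a participation described there as three months, they are reported "spontaneously if considered at least possibly related to rifaximin". The Synopsis gives participation as 3 months of treatment plus 2 months of follow-up. Safety, Adverse Effects reporting and Management reports all SAEs within 24 hours and sets no end date. The SAP adds nothing on the safety observation period.

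**The concern.** The only reason given for observing subjects beyond month 3 is a risk that starts when the drug stops. That reason applies to a subject who stops at Week 4 as much as to one who finishes. Yet the path written for early terminators closes with the visit at which the 3-month data are collected. A case of diarrhea that starts three weeks later would be known only if someone called in.

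The Synopsis makes adverse events the primary safety endpoint, although the Objectives and Endpoints table lists safety under secondary. With 10 treated subjects, one person without post-treatment observation is a tenth of the safety data. A count of zero late events could then mean either that none occurred or that nobody asked.

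The SAE wording raises a second problem that does not depend on dropout: for months 3 to 5 the protocol gives more than one rule on which SAEs must be reported.

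**Working it through.** **Inputs (Protocol).** Planned last dose: Week 12, which the schedule equates with 3 months. Final contact: Week 20, equated with 5 months. Risk window: 2 months after the last dose, taken as 8 weeks to match the schedule. Contacts after baseline: Weeks 1, 3, 5, 7, 9, 11, 12 and 20. Treated subjects: 10.

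**1. The plan's own figure.** For a completer the window ends at 12 + 8 = Week 20, the week of the final call. The plan does what it intends for completers.

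**2. Early stop at Week w.** The window ends at w + 8. If the subject stays on the calendar, the Week 20 call falls 20 - w weeks after the last dose. If the subject takes the Early Term path, nothing is scheduled after that visit.

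| Last dose, Week w | Window ends, w + 8 | Weeks from last dose to Week 20, 20 - w | Contacts in window if kept on calendar (Week) | Contacts scheduled after Early Term visit |
|---|---|---|---|---|
| 1 | 9 | 19 | 3, 5, 7, 9 | 0 |
| 4 | 12 | 16 | 5, 7, 9, 11, 12 | 0 |
| 8 | 16 | 12 | 9, 11, 12 | 0 |
| 11 | 19 | 9 | 12 | 0 |
| 12 (completer) | 20 | 8 | 20 | not applicable |

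Since w is at most 12, 20 - w is at least 8. The calendar schedule therefore always reaches the end of the window. The difference lies between the last two columns, that is, in whether an early terminator stays on the calendar.

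**3. Do the other provisions fill the gap?** Follow-up of an AE or SAE already in progress does not cover an event that begins after termination. The instruction that caregivers call about stool changes applies during the study, and the protocol does not say whether an early terminator is still in it.

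**4. Size.** Ten subjects at 8 weeks each give 10 x 8 = 80 post-dose person-weeks. Each early terminator whose termination visit falls at the last dose removes up to 8 of them (8/80 = 10%). The documents give no dropout rate. Assuming 5% to 30% early termination, the expected loss is 10 x 0.05 x 8 = 4 to 10 x 0.30 x 8 = 24 person-weeks, and the chance of at least one early terminator is 1 - 0.95^10 = 40% to 1 - 0.70^10 = 97%.

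**5. Event rate, for context only.** The protocol cites C. difficile incidences of 0.7% and 1.5% over 6 months of rifaximin in hepatic encephalopathy. At those rates the chance of at least one case among 10 is 1 - 0.993^10 = 6.8% to 1 - 0.985^10 = 14.0%. Population and exposure differ, and the protocol expects a lower risk in subjects without risk factors.

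**6. SAE rules, tested on an unrelated SAE at Week 16.** Week 16 lies between Week 12 and Week 20.
- Synopsis (3 + 2 = 5 months of participation) combined with the during-participation rule: reportable.
- Safety, Adverse Effects reporting and Management (all SAEs, no end date): reportable.
- Serious Adverse Event Reporting, after a three-month participation: not reportable, because it is unrelated.
- Adverse Event Reporting: the event falls within the AE period, which runs to month 5.

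**The case against.** The strongest reply is that silence is not exclusion. The Early Term column lists what is done at that visit and does not cancel Week 20. End of Study Definition promises follow-up to every subject, and the AE period runs to 5 months from first dose with no exception. The protocol also has separate headings for stopping the intervention and for withdrawing from the study, and nothing says that a subject who only stops the drug leaves the schedule. This reading is tenable, and it means that the documents do not show early stoppers to be excluded from follow-up. But no sentence says that the Week 20 call applies to them, and the withdrawal section uses withdrawal and premature discontinuation in one sentence as if they were the same. Two sites of text support two readings that yield different safety data.

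A reader might infer that the fault is the anchor date, because the risk runs from the last dose and the follow-up from the first dose or the planned end. The arithmetic does not support that: Week 20 is never less than 8 weeks after the last dose.

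The SAE sentence governs what goes to the IRB, not what is observed. The Week 20 AE assessment is scheduled regardless, so it should not be inferred that unrelated SAEs in months 3 to 5 would go unrecorded in subjects who reach that call.

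Finally, C. difficile is uncommon, and the exclusion criteria remove subjects with a past infection or recent antibiotics or hospitalization. That lowers the expected number of missed cases. It does not explain why the protocol's own reason for follow-up should hold for completers only.

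**Conclusion.** The point holds as an unresolved ambiguity with a practical consequence. As written, the plan can leave a subject who terminates early without an ongoing event with 0 planned contacts in the 2-month window that the protocol itself names. For completers the window is fully covered. Separately, months 3 to 5 carry conflicting SAE rules for all subjects, and that part needs no assumption about dropout.

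The number affected cannot be derived from the documents. What can be said is 10% of the treated sample per early terminator, assuming that 10 are treated, that dosing ends by Week 12 and that 2 months is 8 weeks. It may be tempting to add that early stoppers mostly leave for poor tolerability, so that the missing observation falls on those at highest risk. The documents give no distribution of reasons, and a subject who leaves with an ongoing AE is followed for that event.

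**What to change.** Reconcile the Synopsis, Overall Design, End of Study Definition, Safety, Adverse Effects reporting and Management, the withdrawal section with its Early Term column, and the AE and SAE reporting sections. In particular:

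- Use one definition of the length of participation, so that AE and SAE collection have the same end.
- Separate stopping the study drug from leaving the study, and use each term for one thing only.
- Show in the schedule whether the Week 20 phone AE assessment, which is already planned, applies to early terminators who still consent to contact, so that the follow-up matches the window the protocol states.

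The cost is protocol wording and at most one further phone contact per early terminator, of a kind already in the schedule. Subjects who withdraw consent or are lost to follow-up cannot be covered by any wording; the safety report should count them separately.

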1 INDICATIONS AND USAGE

To reduce the development of drug-resistant bacteria and maintain the effectiveness of XIFAXAN and other antibacterial drugs, XIFAXAN when used to treat infection should be used only to treat or prevent infections that are proven or strongly suspected to be caused by susceptible bacteria. When culture and susceptibility information are available, they should be considered in selecting or modifying antibacterial therapy. In the absence of such data, local epidemiology and susceptibility patterns may contribute to the empiric selection of therapy.

1.1 Travelers' Diarrhea

XIFAXAN is indicated for the treatment of travelers' diarrhea (TD) caused by noninvasive strains of *Escherichia coli* in adults and pediatric patients 12 years of age and older.

Limitations of Use

XIFAXAN should not be used in patients with diarrhea complicated by fever or blood in the stool or diarrhea due to pathogens other than *Escherichia coli* [see *Warnings and Precautions* (5.1), *Clinical Pharmacology* (12.4), *Clinical Studies* (14.1)].

1.2 Hepatic Encephalopathy

XIFAXAN is indicated for reduction in risk of overt hepatic encephalopathy (HE) recurrence in adults.

In the trials of XIFAXAN for HE, 91% of the patients were using lactulose concomitantly.

CONTRAINDICATIONS

History of hypersensitivity to rifaximin, rifamycin antimicrobial agents, or any of the components of XIFAXAN (4)

WARNINGS AND PRECAUTIONS

- Travelers' Diarrhea Not Caused by *E. coli*: XIFAXAN was not effective in diarrhea complicated by fever and/or blood in the stool or diarrhea due to pathogens other than *E. coli*. If diarrhea symptoms get worse or persist for more than 24 to 48 hours, discontinue XIFAXAN and consider alternative antibiotics (5.1)
- Clostridium difficile*-Associated Diarrhea: Evaluate if diarrhea occurs after therapy or does not improve or worsens during therapy (5.2)
- Hepatic Impairment: Use with caution in patients with severe (Child-Pugh Class C) hepatic impairment (5.4, 8.7)
- Concomitant P-glycoprotein (P-gp) inhibitors (e.g., cyclosporine): Caution should be exercised when concomitant use of XIFAXAN and a P-glycoprotein inhibitor is needed (5.5, 7.1)

ADVERSE REACTIONS

Most common adverse reactions:

- TD (≥2%): Headache (6.1)
- HE (≥10%): Peripheral edema, nausea, dizziness, fatigue, and ascites (6.1)
- IBS-D (≥2%): ALT increased, nausea (6.1)

To report SUSPECTED ADVERSE REACTIONS, contact Salix Pharmaceuticals, a division of Valeant Pharmaceuticals North America LLC, at [name] and www.Salix.com or FDA at [name] or www.fda.gov/medwatch.

DRUG INTERACTIONS

Warfarin: Monitor INR and prothrombin time; dose adjustment of warfarin may be needed to maintain target INR range. (7.2)

USE IN SPECIFIC POPULATIONS

Pregnancy: May cause fetal harm (8.1)

See 17 for PATIENT COUNSELING INFORMATION.

Revised: 01/2018

15 REFERENCES

16 HOW SUPPLIED/STORAGE AND HANDLING

17 PATIENT COUNSELING INFORMATION

*Sections or subsections omitted from the full prescribing information are not listed

Differences in the treatment effect of those patients not using lactulose concomitantly could not be assessed.

XIFAXAN has not been studied in patients with MELD (Model for End-Stage Liver Disease) scores >25, and only 8.6% of patients in the controlled trial had MELD scores over 19. There is increased systemic exposure in patients with more severe hepatic dysfunction [see *Warnings and Precautions* (5.4), *Use in Specific Populations* (8.7), *Clinical Pharmacology* (12.3)].

1.3 Irritable Bowel Syndrome with Diarrhea

XIFAXAN is indicated for the treatment of irritable bowel syndrome with diarrhea (IBS-D) in adults.

2 DOSAGE AND ADMINISTRATION

2.1 Dosage for Travelers' Diarrhea

The recommended dose of XIFAXAN is one 200 mg tablet taken orally three times a day for 3 days.

2.2 Dosage for Hepatic Encephalopathy

The recommended dose of XIFAXAN is one 550 mg tablet taken orally two times a day.

2.3 Dosage for Irritable Bowel Syndrome with Diarrhea

The recommended dose of XIFAXAN is one 550 mg tablet taken orally three times a day for 14 days. Patients who experience a recurrence of symptoms can be retreated up to two times with the same dosage regimen.

**Protocol Title: Pilot, single center, open, trial of rifaximin in
probable Alzheimer's Disease**

NCT Number: NCT03856359

Date: September 6, 2019

Scientific Rationale for Study Design

This is an open label pilot study designed to provide preliminary evidence on the clinical efficacy of rifaximin in improving cognition in AD patients. We will be looking for improvement in test scores, changes in serum levels of neuronal markers and cytokines and changes in gut microbiota following treatment. We will also be collecting data regarding the safety of long-term use of this non-absorbed antibiotic for this disease. This pilot may form the basis for a future larger randomized, double blind controlled study to further test this hypothesis.

Summary statistics will be compiled for mean/SD change from baseline to endpoint on all cognitive, biomarker and microbiome variables. Statistics for cognitive and plasma biomarker tests will be based on nominal p-value of 0.05 given this is a pilot study. We will also examine multiplicity adjusted p-values for correlations between change in cognitive and biomarker/microbiome variables.

Statistical analyses will combined subjects on QD and BID for analyses as this is a pilot study and both doses may impact gut flora. In posthoc analyses we will put dosing as a covariate to examine dose effects.

As such any improvement in cognitive test score and/or significant correlations between cognition and microbiota changes will be viewed as a positive outcome to inform the design of a future larger study.

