Rifaximin (Xifaxan, Salix Pharmaceuticals, Bridgewater, N.J.) (See Package Insert) is a drug that is approved by the FDA for use in humans for the treatment of Hepatic Encephalopathy, Traveler's Diarrhea and Irritable Bowel Syndrome. It is commercially available. It will be used in accordance with approved labeling as pertains to dosage and administration for Hepatic Encephalopathy, contraindications and warnings. However, it will be used investigational in this trial as rifaximin is not FDA approved for the treatment of Alzheimer's Disease.

Safety, Adverse Effects reporting and Management

The AE monitoring schedule is described in the protocol. The drug will be discontinued immediately if there are emergent signs of C.Difficile (e.g. patient has watery diarrhea for longer than 24 hours, fever, abdominal pain or possible bloody stools). All AEs will be assessed by a study physician and referred for appropriate treatment. The study drug may be discontinued at any time per the study physician judgment for safety. All SAEs will be reported to the IRB within 24 hours of becoming aware of the event.

Dosing and Administration

The drug will be administered orally, under supervision of the caregiver, 550 mg twice a day, for 3 months.

Drug Acquisition and Accountability

The drug, rifaximin, will be provided by the study and acquired from the manufacturer. Compliance will be monitored at phone calls and accountability through pill counts at the endpoint study visit.

Formulation, Packaging, Appearance and Labeling

Rifaximin will be packaged in bottles of 100 tablets of 550 mg. The product will be dispensed under the supervision of the study clinician.

Product Storage and Stability

Rifaximin will be stored in the clinical study office in a double locked facility in conditions suitable for its stability.

Preparation

No special measures are required to prepare the drug for oral administration.

Measures to Minimize Bias: Randomization and Blinding

This is an open label pilot study. Objective tests and biomarkers are used to minimize bias.

Study Intervention Compliance

The subject's caregiver will be asked to keep a log of rifaximin dosage and date and time of administration. This will insure compliance and adherence to the study protocol. The compliance log and pill count will be reviewed during the endpoint visit.

Concomitant Therapy

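### The post hoc dosing covariate cannot be read as a dose effect: once-daily dosing is given for a reason, sometimes after treatment starts, and the variable is not defined

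*SAP*

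**What the plan says.** The SAP (Scientific Rationale for Study Design) and the protocol section of the same name combine QD and BID subjects, then state: "In posthoc analyses we will put dosing as a covariate to examine dose effects". Neither defines dosing, names another covariate or mentions the reason for QD.

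The protocol's Overall Design describes a single-site, non-randomized study that consents up to 25 subjects in order to treat 10. On who receives QD it says: "Subjects at risk for drug interactions or tolerability issues may be started and/or maintained on a lower dose of 550 mg once a day". It then assigns QD to subjects on "concomitant drugs which are not contraindicated but known to elevate blood levels SIGNIFICANTLY", and adds "THOSE WITH MILD AEs (E.G. MILD DIARHEA) WILL receive qd dosing BASED ON CLINICIAN JUDGMENT". On early termination: "Subjects who terminate early will receive the 3 month assessment at the time of termination".

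Justification for Dose and Study Population says "The dose will remain the same throughout the 3 month study of rifaximin administration unless stopped for safety reasons" and, in the next sentence, "The dose can be stopped or temporarily reduced for safety or tolerability reasons based on clinical judgment". The withdrawal section lets a subject who interrupted the drug be asked to resume it. Dosing and Administration mentions BID only: "The drug will be administered orally, under supervision of the caregiver, 550 mg twice a day, for 3 months". The Exclusion Criteria rule out subjects taking medications that interact with rifaximin, and Concomitant Therapy permits only medications that do not interact.

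Study Intervention Compliance provides a caregiver log of dosage, date and time, plus a pill count at the endpoint visit. A case report form (CRF) page records the date and reason for discontinuation. No section says the same for a dose reduction, although the full CRF is not among the documents.

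**The concern.** A dose coefficient has a dose interpretation only if QD and BID subjects are otherwise comparable. Here the protocol describes no route to QD without a reason, so every QD subject has one, while BID subjects may or may not. Co-medication burden, expected intolerance or an AE could each be related to change in ADAS-Cog or the biomarkers whatever the dose. The mild-AE route adds a second problem. If rifaximin caused the AE, the covariate is partly an outcome of treatment.

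A third problem is coding. Starting, final, ever-reduced and average dose can put the same subject in different groups, and the SAP does not choose among them. What is at stake is a figure labelled as a dose effect that partly reflects why subjects were on QD and how the analyst coded them. The pilot is meant to inform a larger study, so that figure could be carried forward.

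**Working it through.** The plan gives no figure for the dose comparison, and no expected QD share, SD or effect size, so there is nothing to reproduce. From the documents: 10 treated subjects, nominal 0.05 (two-sided assumed) and 12 weeks of treatment. QD/BID splits, overlap and shifts below are assumptions.

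**1. Precision without adjustment.** With a QD and b BID subjects, half-width = t(8) × √(1/a + 1/b) SD, where t(8) = 2.306.
- 5/5: 2.306 × √0.400 = 1.46 SD
- 3/7: 2.306 × √0.476 = 1.59 SD
- 2/8: 2.306 × √0.625 = 1.82 SD
- 1/9: 2.306 × √1.111 = 2.43 SD

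**2. Will there be any QD subjects?** If each subject has chance p of being on QD, P(none) = (1 − p)^10. That is 35% at p = 0.10, 11% at 0.20 and 3% at 0.30. At p = 0.10 the chance of at most one is 0.349 + 10 × 0.1 × 0.9^9 = 74%.

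**3. Adjustment for a yes/no reason for QD.** Let m BID subjects have a reason. All QD subjects have one, so the dose coefficient equals the QD mean minus the mean of those m subjects. Half-width = t(7) × √(1/a + 1/m), where t(7) = 2.365.

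| Split | m = 0 | m = 1 | m = 2 | m = 4 |
|---|---|---|---|---|
| 2/8 | not estimable | 2.90 SD | 2.36 SD | 2.05 SD |
| 5/5 | not estimable | 2.59 SD | 1.98 SD | 1.59 SD |

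At m = 0 the reason and QD columns are identical (rank 2 of 3), and this is so at any sample size. The other cells treat the reason as one baseline factor. An AE-driven reason is post-baseline, so these figures describe precision only and do not show that adjustment would remove the bias.

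**4. Illustrative bias.** If having a reason shifts the outcome by s and dose does nothing, the unadjusted contrast is off by s × (1 − m/b). For s = 0.5 SD this is 0.50 SD at no overlap, 0.5 × 0.75 = 0.375 SD at 2/8 with m = 2, and 0.5 × 0.2 = 0.10 SD at 5/5 with m = 4. At no overlap the chance of p < 0.05 (noncentral t, 8 df) is 8.7% at 2/8 and 10.8% at 5/5. The formula gives all reasons one common baseline shift, and nothing in the documents supplies s.

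**5. Coding.** At full adherence, BID is 12 × 14 = 168 tablets and QD is 12 × 7 = 84. A lasting switch to QD at the week 11 call gives 11 × 14 + 7 = 161 tablets, 96% of full BID. That subject is BID by starting dose and QD by final dose. Conversely, 84 tablets fits a QD completer, a BID subject who stopped at week 6 (6 × 14 = 84) and a BID subject who took half the doses for 12 weeks. A pill count alone cannot identify dose.

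**The case against.** The strongest reply is that little depends on this model. It is labelled post hoc in a pilot, the main analysis pools the doses, and the SAP's definition of a positive outcome rests on cognitive improvement or cognition–microbiota correlations, with no dose term. That stands, and it limits the weight of the point. A reader might infer that the trial's efficacy conclusion is compromised; the documents do not support that. Nor do they show that the bias is large: no passage links co-medication or mild diarrhea to 12-week ADAS-Cog change.

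A second reply is that AE assessments, medication records and the caregiver log let much of the reason for QD be reconstructed and adjusted for. Reconstruction is partly feasible, but it does not cure the problem. A reader might infer that sample size is the main obstacle and that a larger trial with the same dosing rule would be safe. That does not follow, because missing overlap and a post-baseline reason do not shrink with more subjects.

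A third reply is that the dosing passages can be read together. In part they can. The adjacent sentences in Justification for Dose and Study Population can be rule and exception, and the BID-only section can be the nominal regimen. A reader might call these flat contradictions; that goes too far, and they need clarification. The conflict over interacting drugs is different, because one section retains subjects on level-raising drugs while two others exclude or disallow interacting ones.

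**Conclusion.** The point holds in a limited form. As written, the plan yields a dose coefficient that is confounded with the reason for QD, is partly post-baseline through the AE route, and depends on an unstated coding. Adjustment does not restore a dose interpretation. Even apart from bias, the contrast is very imprecise (about ±1.5 to ±2.4 SD for splits from 5/5 to 1/9), and there may be no QD subject at all. The confounding and the missing definition follow from the text. The interval widths depend on the assumed splits, and any bias size is illustrative only. The primary pooled result is untouched; the risk is a misleading dose statement passed on to the larger study. Separately, the conflict on interacting drugs affects who is eligible and who is on QD.

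**What to change.** Keep the pooled main analysis. In the SAP and the matching protocol paragraph, replace the dose-effect aim with:
- a descriptive summary of change by assigned starting dose, with early terminators shown separately because they are assessed at termination;
- a listing of every QD, dose-reduced or interrupted subject with reason, date and tablets taken from the caregiver log.

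If a covariate model is kept, use assigned starting dose as its single defined variable. It is fixed before treatment, though still confounded. Add a sentence such as: *The coefficient is confounded by the reason for once-daily dosing and will not be interpreted as a dose effect.* Any average-dose variable must say how interruption days and missed doses count, and should be described as exposure, not dose alone. Record the reason and date of each dose reduction if the CRF does not already do so.

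In the protocol, reconcile Overall Design with the Exclusion Criteria and Concomitant Therapy on interacting or level-raising drugs. Clarify how the two sentences on dose change and the BID-only section fit with Overall Design. Which rule applies is for the investigators.

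The cost is an SAP paragraph, a listing, possibly one CRF field and the protocol clarifications. The downside is that the dose-effect reading is given up.
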